Original Protocol	30-Nov-2017	Not applicable

[Redacted text block]

[Redacted text block]

[Redacted text block]

[Redacted text block]

[Redacted text block]

SUMMARY OF KEY CHANGES FOR REVISED PROTOCOL 01		
Section Number & Title	Description of Change	Brief Rationale
[REDACTED]	Added note: On 18 October 2019, the PDCO adopted a positive opinion on BMS' PIP request for a full product-specific waiver (EMA-001191-PIP01-11-M03) on the grounds that clinical studies with DAKLINZA cannot be expected to be of significant therapeutic benefit to or fulfil a therapeutic need of the specified paediatric subsets. As a result, BMS will terminate Study AI444423 early.	[REDACTED]
[REDACTED]	Added note: With regard to paediatric HCV treatment regimens, all-oral, pangenotypic, non-DCV containing regimens, are being developed with the intention to commercialize them in the context of their existing adult MA; these regimens are more advanced in their development than the DCV+SOF regimen, the regimen being investigated in this study. In this context, on 18 October 2019, the PDCO of the EMA adopted a positive opinion on BMS' PIP request for a full product-specific waiver (EMA-001191-PIP01-11-M03) on the grounds that clinical studies with DAKLINZA cannot be expected to be of significant therapeutic benefit to or fulfil a therapeutic need of the specified paediatric subsets. As a result, BMS will terminate Study AI444423 early.	[REDACTED]
Section 4 Objectives and Endpoints	Added note: With the early termination of this study, previously collected data to address PK, SVR, and select safety assessments (e.g. AEs, laboratory tests, end of treatment subject status) will be reported only within adolescent participants 12 to <18 years of age. The secondary objectives related to assessment of genotypic substitutions associated with virologic failure and the acceptability and palatability of the daclatasvir formulations and the exploratory objective regarding durability of response will not be reported.	[REDACTED]
Section 5.1 Overall Design	Addition of note: Due to the early termination of the study, only participants 12 to <18 years of age were enrolled in the study into Cohort 1; no participants will be enrolled in Cohorts 2 and 3. The duration of the Long-Term Follow-Up period for these participants will be less than the initially planned 96 weeks. Upon approval of this revised protocol, participants will return to the study center to conduct an EOS visit.	[REDACTED]
Section 5.2 Number of Participants	Addition of note: Although the original protocol provided for a total of 30 participants, only 5 participants, limited to Cohort 1, will have been enrolled in the study, as the result of the early termination of this study.	[REDACTED]

SUMMARY OF KEY CHANGES FOR REVISED PROTOCOL 01		
Section Number & Title	Description of Change	Brief Rationale
[REDACTED]	Added note: Due to the early termination of the study, only 5 participants 12 to <18 years of age were enrolled in the study into Cohort 1; the duration of the Long-Term Follow-Up period for these participants will be less than the initially planned 96 weeks. No participants will be enrolled in Cohorts 2 and 3.	[REDACTED]
Section 6.1 Inclusion Criteria	Added limitation of enrollment to Cohort 1 participants \geq 45 kg on Day 1	[REDACTED]
Section 7.1 Treatments Administered	Updated text with the limitation of participants in Cohort 1 to participants \geq 45 kg on Day 1 Added note: Due to the early termination of the study, participants will only have been enrolled in Cohort 1 and administered the adult formulations of DCV and SOF (60 mg dose of DCV and 400 mg dose of SOF). No paediatric formulations will be administered in the study. Added footnote to Table 7.1-1 to clarify that adult formulation would only be administered to participants in Cohort 1 who were required to be \geq 45kg	[REDACTED]
Section 8.1.1 Post Study Treatment Follow Up	Clarified duration of follow up period for participants who discontinue as 'completion of the designated follow up period' versus 'conclusion of study'	[REDACTED]
Section 8.2 Discontinuation from the Study	Added that follow-up procedures should be completed prior to initiation of alternate HCV therapy	[REDACTED]
Section 9.2.1 Time Period and Frequency for Collecting AE and SAE Information	Added SOF SmPC as reference safety information	[REDACTED]
Section 9.4.4 Clinical Safety Laboratory Assessments	Added note: All laboratory assessments scheduled for the Post-Treatment Week 108 visit should be performed at the EOS visit.	[REDACTED]

SUMMARY OF KEY CHANGES FOR REVISED PROTOCOL 01		
Section Number & Title	Description of Change	Brief Rationale
Section 9.8.2.1 HCV Virologic Resistance Testing	Added note that resistance testing will not be performed on Baseline samples	[REDACTED]
Section 9.8.2.3 Brief Questionnaire/Interim Phone Contact	Added note: Due to the early termination of the study, participants will perform an EOS visit and interim telephone contact will not be necessary after the EOS visit.	[REDACTED]
Section 10.1 Sample Size Determination	Added note: Not Applicable due to the early termination of the study; a total of 5 participants will have been enrolled in the study into Cohort 1.	[REDACTED]
Section 10.3 Statistical Analyses	Added note: With the early termination of this study, previously collected data to address PK, SVR, and select safety assessments (e.g. AEs, laboratory tests, end of treatment subject status) will be reported only within adolescent participants 12 to <18 years of age. Given the small number of subjects enrolled in the study, no statistical analyses will be performed. Genotypic substitution(s) associated with virologic failure and the acceptability and palatability of the DCV formulations will not be reported. Likewise, an interim analysis will not be performed.	[REDACTED]
Section 10.3.2 Resistance Analyses	Added note: These data will not be reported because the prevalence of the relevant RAV varies from 4-10% and as such might not be detected at Baseline in a sample size of 5 participants. As of 18 October 2019, all participants had completed at least 41 weeks of post-treatment follow-up and none had experienced virologic failure.	[REDACTED]
Section 10.3.5.1 Acceptability and Palatability Assessments of Daclatasvir Formulations	Added note: These data will not be reported as only the adult formulation was administered in the study and there is no value to perform an analysis of the adult formulation	[REDACTED]
Section 10.3.6 Interim Analysis	Added note: An interim analysis will not be performed. As only 5 subjects will be enrolled in this study, analyses are not needed to guide dosing for additional participants.	[REDACTED]
Appendix 5	Updated version of DIADS table from December 2004 to July 2017 version 2.1 of DAIDS Table for Grading the Severity of Adult and Pediatric Adverse Events	[REDACTED]

█ [REDACTED]

█ [REDACTED]

█ [REDACTED]

TABLE OF CONTENTS

TITLE PAGE	1
DOCUMENT HISTORY	3
[REDACTED]	[REDACTED]
SUMMARY OF KEY CHANGES FOR REVISED PROTOCOL 01	5
TABLE OF CONTENTS	10
1 SYNOPSIS	13
2 SCHEDULE OF ACTIVITIES	19
[REDACTED]	[REDACTED]
[REDACTED]	[REDACTED]
[REDACTED]	[REDACTED]
[REDACTED]	[REDACTED]
4 OBJECTIVES AND ENDPOINTS	31
5 STUDY DESIGN	31
5.1 Overall Design	31

1 SYNOPSIS

Protocol Title: Open-Label, Single-Arm Trial to Evaluate the Pharmacokinetics, Safety and Efficacy of Daclatasvir (DCV) in Combination with Sofosbuvir (SOF) in Children from 3 to less than 18 Years of Age with GT-1 to -6 Chronic Hepatitis C (CHC) Infection

Study Phase: 2

[REDACTED]

[REDACTED]

[REDACTED]

- [REDACTED]
- [REDACTED]
- [REDACTED]
- [REDACTED]
- [REDACTED]

[REDACTED]

[REDACTED]

Study Population:

Paediatric patients (3 years to < 18 years of age) monoinfected with Hepatitis C virus (genotypes (GT)-1 to -6) who are non-cirrhotic and either treatment-naïve or treatment-experienced.

Note: With the early termination of the study, only adolescent participants 12 to <18 years of age will have been enrolled in the study.

Objectives and Endpoints:

Note: With the early termination of this study, previously collected data to address PK, SVR, and select safety assessments (e.g. Adverse Events (AEs), laboratory tests, end of treatment subject status) will be reported only within adolescent participants 12 to <18 years of age. The secondary objectives related to assessment of genotypic substitutions associated with virologic failure and the acceptability and palatability of the daclatasvir formulations [redacted] will not be reported.

Objectives	Endpoints

Primary
 
 To evaluate the PK profile of DCV in combination with SOF in children and adolescents aged 3 to <18 years of age 	
 Pharmacokinetic parameters (C_{min}, C_{max}, T_{max}, AUC (TAU), CLT/F) for DCV derived from plasma concentration versus time data on Day 10 (+/-3 days) within a dosing interval. In Cohort 3 (ages 3 to <6 years of age); PK parameters will be assessed using model-based analyses with 5 samples from each participant.

Secondary
 
 To assess the safety and tolerability of the DCV+SOF regimen in paediatric participants To determine the proportion of participants with SVR12 	
 Frequencies of serious adverse events (SAEs), adverse events (AEs) leading to discontinuation of study therapy, AEs by intensity, and laboratory abnormalities by toxicity grade on treatment and during follow-up Proportion of participants with HCV RNA <LLOQ (TD or TND) at post-treatment follow-up Week 12

Objectives	Endpoints

 To evaluate genotypic substitution(s) associated with virologic failure To assess the acceptability and palatability for the age-appropriate chewable tablet formulation, and acceptability for adult film-coated tablet 	
 Frequencies of NS5A and NS5B resistance-associated variants (RAVs) emergent at the time of virologic failure on treatment and during follow-up in non-responders Summary of responses from questionnaire assessing acceptability and palatability at Day 1, Week 4, and Week 12

[REDACTED]
	
[REDACTED]

[REDACTED]
	
[REDACTED]

Overall Design:

The study will be an open-label, single-arm, descending-age cohort trial evaluating the PK profile, safety, tolerability, and efficacy of DCV+SOF administered for 12 weeks to paediatric participants (3 < 18 years of age) with CHC virus infection.

Enrolment will begin with Cohort 1, followed by Cohorts 2 and 3.

- Cohort 1: 12 to < 18 years of age
- Cohort 2: 6 to < 12 years of age
- Cohort 3: 3 to < 6 years of age

Note: Due to the early termination of the study, only participants 12 to <18 years of age were enrolled in the study into Cohort 1; no participants will be enrolled in Cohorts 2 and 3.

Samples for assessment of DCV PK will be collected on Day 10 of the study. In each cohort, DCV PK will be evaluated after the initial 5 participants complete their Day 10 visit in order to determine if the target DCV exposure is achieved.

Enrolment in Cohorts 2 and 3 will be dependent on the availability of the European Commission (EC) approved SOF age appropriate dose and formulation for the corresponding age cohort.

Post treatment, participants will be followed for 12 weeks to assess sustained virologic response at Post-treatment Week 12 (SVR12) and then for an additional 2 years (96 weeks) as long-term follow-up to assess [REDACTED], durability of response, long-term safety, and the persistence of resistance variants in non-responders.

Note: With the early termination of this study, participants will not complete the initially planned 96 weeks of LTFU. As of 18 October 2019, all participants will have completed their Post Treatment Week 24 visit and approximately 41 to 53 weeks of post-treatment follow-up;

participants will be asked to return to the study site to perform an EOS visit upon approval of the revised protocol.

Number of Participants:

A minimum of 30 participants will be evaluated for the primary endpoint (PK), and assigned to 3 age-descending cohorts (12 to <18 years of age, 6 to < 12 years of age and 3 to < 6 years of age); at least 8 participants will be treated in each age cohort.

Note: Although the original protocol provided for a total of 30 participants, only 5 participants, limited to Cohort 1, will have been enrolled in the study as the result of the early termination of this study.

For further information regarding sample size determination, please refer to [Section 10.1](#).

Treatment Arms and Duration:

This will be a single-arm study in which participants will be administered DCV+SOF QD for 12 weeks.

Study treatment:

[figure not shown]
Product Description / Class and Dosage Form	Potency	IP/ Non-IMP	Blinded or Open Label	Packaging / Appearance	Storage Conditions (per label)
Daclatasvir ^a (BMS-790052-05/DCV) Film Coated Tablet	60 mg (as the free base)	IP	Open	Bottle Each tablet is plain, green, biconvex, pentagonal and film-coated.	Store per IP Label.
Daclatasvir Dihydrochloride Chewable Tablet	20 mg	IP	Open	Blister A white to off white, flat, plain oval tablet	Store per IP Label.
Daclatasvir Dihydrochloride Chewable Tablet	10 mg	IP	Open	Blister A white to off white, flat, plain round tablet	Store per IP Label.
Daclatasvir Dihydrochloride Chewable Tablet	5 mg	IP	Open	Blister A white to off white, flat, plain round tablet	Store per IP Label.
Sofosbuvir ^b , (SOF) Film Coated Tablet	400 mg	IP	Open	Bottle Yellow, capsule-shaped, film-coated tablets debossed with “GSI” on one side and “7977” on the other side	Store per IP Label
Sofosbuvir (SOF) (paediatric formulation, TBD)	50 mg	IP	Open	TBD	Store per IP Label

^a Daclatasvir clinical presentation, adult formulation

^b Sofosbuvir adult formulation

Note: Due to the early termination of the study, participants will only have been enrolled in Cohort 1 and administered the adult formulations of DCV and SOF. The paediatric formulations will not be administered in the study.

Study Schematic:

The total duration of the study for each participant is approximately 2.5 years:

- Screening: 42 days
- Treatment Duration: 12 weeks
- Post-Treatment Follow-up Duration: Upon completion of the Post-treatment Week 12 visit, participants will be followed for an additional 2 years (96 weeks) as long-term follow-up to assess SVR24, durability of response, long term safety, and the persistence of resistance variants in non-responders.

Note: With the early termination of this study, the duration of the study for participants will be less than 2.5 years; participants will not complete the initially planned 96 weeks of long-term follow-up. As of 18 October 2019, all participants will have already completed their Post Treatment Week 24 visit and approximately 43 to 51 weeks of post-treatment follow-up. Upon approval of the revised protocol, participants will be asked to return to the study site to perform an EOS visit.

The dose of DCV will be determined according to the weight of the participant prior to dosing on Day 1; the dose will not be adjusted to weight over the course of the study.

DCV should be administered as the adult film-coated 60-mg tablet formulation to adolescent participants 12 to < 18 years of age (Cohort 1 who are ≥ 45 kg) and as a paediatric chewable-tablet formulation (5, 10, 20 mg) to all participants < 12 years of age (Cohorts 2 and 3) according to [Table 7.1-1](#).

The SOF dose administered will be the dose and formulation approved by the European Commission for the corresponding age cohort. Cohort 1 will receive the 400-mg adult

formulation. Enrollment in Cohorts 2 and 3 will begin following EC approval of the age appropriate dose and formulation for SOF for those respective age groups.

Doses of DCV and SOF assigned on Day 1 cannot be modified but can be interrupted or discontinued to manage adverse events. In the event of interruption or discontinuation, both DCV and SOF must be stopped simultaneously. DCV+SOF treatment can be interrupted for a maximum of 7 days, and if not restored after 7 days, the treatment should be permanently discontinued.

Note: DCV dose modification will only be permissible if PK data from the initial 5 participants in the cohort suggest that the dose administered does not achieve the desired exposure criteria. The sponsor will advise how to modify the dose of DCV being administered, if needed.

Note: With the early termination of this study, only the adult formulations of DCV and SOF will be administered in this study.

2 SCHEDULE OF ACTIVITIES

Table 2-1: Screening Procedural Outline (AI444423)

Procedure	Screening Visit ^a	Notes
Eligibility Assessments		
Informed Consent and Assent (where applicable)	X	
Inclusion/Exclusion Criteria	X	
Medical History	X	To include route of HCV transmission and prior response to anti-HCV medications, if applicable
HCV Serology	X	
HCV RNA and backup HCV RNA sample	X	
HCV Genotype	X	
HIV, HBV Serology	X	
Alpha fetoprotein (AFP)	X	
Assessment of liver fibrosis status by liver biopsy, Fibroscan or Serologic test (APRI [AST to platelet ratio index])	X	Refer to Section 6.2 for fibrosis determination criteria and timing of assessments
Safety Assessments		
Physical Examination	X	
Physical Measurements	X	Height and weight
Vital Signs	X	Includes body temperature, respiratory rate, and seated blood pressure and heart rate. Blood pressure and heart rate should be measured after the participant has been at rest
Serious Adverse Events Assessment	X	Report SAEs that occur after consent is obtained
Concomitant and Previous Medication Use	X	Refer to Section 7.7.1 for details
Laboratory Tests	X	Fasting not required, see Section 9.4.4
ECG, Single 12-Lead	X	ECG should be recorded after the participant has been at rest

Table 2-1: Screening Procedural Outline (AI444423)

Procedure	Screening Visit ^a	Notes
Pregnancy Test FOCBP only	X	Urine pregnancy test (minimum sensitivity equivalent units 25 IU/L or equivalent units of HCG); Collect serum sample if urine is positive. Pregnancy test should be repeated within 24 hours prior to first dose of study treatment
Obtain participant number via IRT	X	

^a All screening procedures, except where noted, must be completed within 42 days of the screening visit

Table 2-2: On Treatment Procedural Outline (AI444423)					
Procedure	Day 1 Visit	During Treatment Day 10 (± 3 days)	During Treatment Weeks 4 and 8 (± 3 days)	End of Treatment/ Week 12 (± 3 days)/Early Discontinuation	Notes
Eligibility Assessments					
Inclusion/Exclusion Criteria	X				Review eligibility criteria prior to treatment to ensure requirements are met
Safety Assessments					
Targeted Physical Examination	X		X	X	Should include assessment of heart, lung, and abdomen
Physical Measurements	X	X	X	X	Height and weight
Vital Signs	X	X	X	X	Includes body temperature, respiratory rate, and seated blood pressure and heart rate; blood pressure and heart rate should be measured after the participant has been at rest
Serious Adverse Event Assessment	X	X	X	X	
Adverse Events Assessment	X	X	X	X	AE assessment begins after Day 1 study treatment administration
Concomitant Medication Use	X	X	X	X	See Section 7.7.1
Laboratory Tests	X	X	X	X	Fasting not required. See Section 9.4.4
Pregnancy Test FOCBP only	X		X	X	Urine pregnancy test (minimum sensitivity equivalent units 25 IU/L or equivalent units of HCG); results of urine test, performed within 24 hours of first dose, should be negative prior to dosing

Table 2-2: On Treatment Procedural Outline (AI444423)					
Procedure	Day 1 Visit	During Treatment Day 10 (± 3 days)	During Treatment Weeks 4 and 8 (± 3 days)	End of Treatment/ Week 12 (± 3 days)/Early Discontinuation	Notes
Efficacy Assessments					
HCV RNA and backup HCV RNA	X	X (primary tube required; backup sample optional)	X	X	Participants with indeterminate HCV RNA testing or with suspected on treatment failure (HCV virologic breakthrough) will be retested for HCV RNA, HCV genotype, and HCV resistance along with PK trough levels at an unscheduled visit as soon as possible before their next regular visit
HCV Resistance and back up HCV Resistance	X	X (primary tube required; backup sample optional)	X	X	
HCV Genotype	HCV Genotype sample to be collected at time of HCV RNA sample collection to confirm suspected virologic breakthrough/other on-treatment failure				
Other Assessments					
	X				
Serial Blood PK of DCV and trough levels of SOF and its metabolites (all participants)		X			See Section 9.5
Trough Blood PK: DCV, SOF and its metabolites (all participants)			X	X	See Section 9.5

Table 2-2: On Treatment Procedural Outline (AI444423)					
Procedure	Day 1 Visit	During Treatment Day 10 (± 3 days)	During Treatment Weeks 4 and 8 (± 3 days)	End of Treatment/ Week 12 (± 3 days)/Early Discontinuation	Notes
Acceptability and Palatability Questionnaire	X		X	X	Day 1, Week 4, and Week 12/ End of treatment/Early Discontinuation, See Section 9.8.2.2
Brief Questionnaire	X			X	A brief questionnaire will be completed by the participant/guardian to include contact details such as email address, primary care physician, and 2 non-residing contacts in case the participant/guardian cannot be reached for their study assessments unless prohibited by local laws or regulations
Study Treatment					
Register eligible participants for treatment via IRT	X				Day 1 age and weight to be used for determining formulation and dose
Dispense Study Treatment and on-site dosing	X	X	X ^a		Study treatment should be administered in office at all study visits and after trough PK sample collection on all visits after Day 1
Assessment of Study Medication Use/Treatment Compliance		X	X	X	See Section 7.6

^a If the participant cannot attend the Treatment Week 12 visit as scheduled, the participant should complete treatment on Day 84. Treatment Week 12 assessments should be conducted once the participant returns to the site and no additional dispensing or dosing will occur on this visit. Similarly drug dispensing and dosing will not occur for those participants that discontinue early from the study

Table 2-3: Post-Treatment Long-term Procedural Outline (AI444423)

Procedure	Post-Treatment Week 4 (± 7 days)	Post-Treatment Weeks 12 and 24 (± 7 days)	Post-Treatment Weeks 48, 72, 96 (± 6 weeks)	Post-Treatment Week 108/ End of Study (± 6 weeks)	Notes
Safety Assessments					
Targeted Physical Examination	X			X	Should include assessment of heart, lung, and abdomen
Physical Measurements	X	X	X	X	Height and weight
Vital Signs	X	X	X	X	Includes body temperature, respiratory rate, and seated blood pressure and heart rate. Blood pressure and heart rate should be measured after the participant has been at rest.
Serious Adverse Events Assessment	X	X	X	X	Only SAEs related to study drug or protocol-specified procedure(s) should be reported after Post-Treatment Week 4.
Adverse Events Assessment	X				
Hepatic disease progression	X	X	X	X	Development of cirrhosis and/or its complications
Laboratory Tests	X	X	X	X	Fasting not required
Pregnancy Test FOCBP only	X				Post-Treatment Week 4 only. Urine pregnancy test; collect serum if urine is positive
Efficacy Assessments					
HCV RNA and backup HCV RNA sample	X	X	X	X	Participants with suspected relapse will have samples collected to retest HCV

Table 2-3: Post-Treatment Long-term Procedural Outline (AI444423)

Procedure	Post-Treatment Week 4 (± 7 days)	Post-Treatment Weeks 12 and 24 (± 7 days)	Post-Treatment Weeks 48, 72, 96 (± 6 weeks)	Post-Treatment Week 108/ End of Study (± 6 weeks)	Notes
HCV Resistance and backup HCV Resistance	X	X	X	X	RNA, HCV genotype, and HCV resistance at an unscheduled visit as soon as possible before their next regular visit
HCV Genotype	HCV Genotype sample to be collected at time of HCV RNA sample collection for suspected relapse to evaluate for possible re-infection/relapse				
Other Assessments					
Confirm Brief Questionnaire Responses ^a	X	X	X	X	
Interim Phone Contacts	Required on a quarterly basis in between office visits (ie, post-treatment Week 36, 60, and 84 (± 2 weeks)). The purpose of the phone contact is to verify the participant's continuation in the study and to confirm the next study visit.				

^a Applicable where local regulations permit

Note: Upon approval of Revised Protocol 01, participants should perform an End of Study visit and do not need to complete any other post-treatment visits if not yet conducted.

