9 STUDY ASSESSMENTS AND PROCEDURES

- Study procedures and timing are summarized in the Schedule of Activities ([Section 2](#)).
- Protocol waivers or exemptions are not allowed.
- All immediate safety concerns must be discussed with the Sponsor immediately upon occurrence or awareness to determine if the participant should continue or discontinue treatment.
- Adherence to the study design requirements, including those specified in the Schedule of Activities (Section 2), is essential and required for study conduct.
- All screening evaluations must be completed and reviewed to confirm that potential participants meet all eligibility criteria prior to dosing. The investigator will maintain a screening log to record details of all participants screened and to confirm eligibility or record reasons for screening failure, as applicable.
- Procedures conducted as part of the participant's routine clinical management (eg, blood count) and obtained before signing of informed consent may be utilized for screening or baseline purposes provided the procedure meets the protocol-defined criteria and has been performed within the timeframe defined in the Schedule of Activities (Section 2).

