9.2.1 Time Period and Frequency for Collecting AE and SAE Information

The collection of nonserious AE information should begin at initiation of study treatment and at the time-points specified in the Schedule of Activities ([Section 2](#)). Nonserious AE information should also be collected from the start of a placebo lead-in period or other observational period intended to establish a baseline status for the participants.

Section 4.8 of the DCV SmPC¹³ and/or SOF SmPC⁸ represent the reference safety information for the DCV+SOF regimen to determine expectedness of serious adverse events for expedited reporting. Following the participant's written consent to participate in the study, all SAEs, whether related or not related to study drug, must be collected, including those thought to be associated with protocol-specified procedures.

All SAEs must be collected that occur during the screening period and within 30 days of discontinuation of dosing.

The investigator must report any SAE that occurs after these time periods that is believed to be related to study drug, protocol-specified procedure or hepatic disease progression (i.e. development of liver cirrhosis and/or its complications).

- Medical occurrences that begin before the start of study treatment but after obtaining informed consent will be recorded on the appropriate section of the eCRF section.
- All SAEs will be recorded and reported to Sponsor or designee within 24 hours, as indicated in [Appendix 3](#).
- The investigator will submit any updated SAE data to the sponsor within 24 hours of this being available.

Investigators are not obligated to actively seek AEs or SAEs in former study participants. However, if the investigator learns of any SAE, including a death, at any time after a participant has been discharged from the study, and he/she considers the event reasonably related to the study treatment or study participation, the investigator must promptly notify the sponsor.

The method of evaluating, and assessing causality of AEs and SAEs and the procedures for completing and reporting/transmitting SAE reports are provided in [Appendix 3](#).

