6.6.3 Hepatic Disease Progression

Hepatic disease progression is summarized by the categories specified in Table 6.6.3-1 during the on-treatment and follow-up analysis periods combined for treated participants. Hepatic disease progression is identified from the Hepatic Related Diagnoses CRF.

Table 6.6.3-1: Hepatic Disease Progression Diagnoses

Diagnoses

Cirrhosis, non-bleeding esophageal varices, bleeding esophageal varices, hepatic encephalopathy, hepatocellular carcinoma, spontaneous bacterial peritonitis, non-bleeding gastric varices, bleeding gastric varices, hepatorenal syndrome, liver transplant

A by-participant listing of hepatic disease progression is provided for enrolled participants.

b Cut-off applies to frequency of participants with preferred terms in any cohort.

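### Table 2-3 leaves out hepatic-progression SAEs that Section 9.2.1 requires after treatment, so a site following the schedule literally could fail to report one

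*Protocol*

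**What the plan says.** Three places in the current protocol govern SAE reporting after treatment.

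- **Table 2-3**, note to the SAE row: "Only SAEs related to study drug or protocol-specified procedure(s) should be reported after Post-Treatment Week 4". The row is marked at every post-treatment visit, including End of Study. The visit that sets the limit has a window of 7 days either side.
- **Section 9.2.1** sets an all-cause period: "All SAEs must be collected that occur during the screening period and within 30 days of discontinuation of dosing". After that, the investigator must report any SAE "believed to be related to study drug, protocol-specified procedure or hepatic disease progression", which the section explains as cirrhosis or its complications. Reports are due within 24 hours.
- **Appendix 3** asks for SAEs within 24 hours whatever their relation to treatment, and states no end of period.

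Two further provisions matter. Table 2-3 has a separate hepatic-progression row at every post-treatment visit, described as "Development of cirrhosis and/or its complications". SAP Section 6.6.3 takes its summary from a dedicated form: "Hepatic disease progression is identified from the Hepatic Related Diagnoses CRF".

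On the standing of the schedule, Section 9 says: "Adherence to the study design requirements, including those specified in the Schedule of Activities (Section 2), is essential and required for study conduct". The same section describes the schedule as a summary of procedures and timing. Neither document says which text governs if the schedule and a section disagree.

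**The concern.** The first word of the Table 2-3 note is restrictive. Read literally, it removes an SAE that is due to hepatic progression but is not attributed to drug or procedure. Section 9.2.1 makes that same SAE mandatory. A site can comply with the schedule and still breach the section.

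At stake is SAE reporting for a narrow class of event: serious, caused by liver disease progression, and judged unrelated to drug and procedure. Such an event might not reach the sponsor within 24 hours, and might be missing from the follow-up SAE frequency. That frequency belongs to a secondary endpoint in Table 4-1, and AEs are among the data still to be reported after early termination. Section 8.1.1 names long-term safety as a key endpoint.

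The instruction is still in use. Participants return for an EOS visit under the revised protocol, and SAE assessment is scheduled at that visit.

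**Working it through.** The plan states no figure on this point to reproduce. The check compares the texts and then does the day arithmetic.

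**1. Which SAEs are reportable once the all-cause period has ended**

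| SAE attributed to | Table 2-3 note | Section 9.2.1 | Appendix 3 |
|---|---|---|---|
| Study drug | Report | Report | Report |
| Protocol-specified procedure | Report | Report | Report |
| Hepatic progression only | Excluded | Report | Report |
| None of these | Excluded | Not required | Report (no end of period stated) |

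The third line is the direct conflict. The fourth shows that Appendix 3, read alone, matches neither of the other two.

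One concrete case: SAP Table 6.6.3-1 counts hepatocellular carcinoma among the progression diagnoses, and Appendix 3 requires cancer to be handled as an SAE. If the investigator judged it unrelated to drug and procedure, the Table 2-3 note would exclude it.

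**2. Whether the hepatic row replaces SAE reporting**

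It does not. The row is an assessment and carries no reporting instruction. Under Appendices 2 and 3, SAEs go on the SAE form, with 24-hour reporting. SAP Table 6.6.2-1 summarises SAEs separately for follow-up, whereas SAP Section 6.6.3 summarises hepatic progression over treatment and follow-up combined. The hepatic form keeps the diagnosis but not the SAE report.

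**3. When the all-cause period ends**

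Inputs: Post-Treatment Week 4 with its 7-day window (Table 2-3), and 30 days after dosing (Section 9.2.1).

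- Nominal visit day: 4 × 7 = 28. Difference from the 30-day rule: 30 − 28 = 2 days shorter.
- Earliest visit: 28 − 7 = day 21. Difference: 30 − 21 = 9 days shorter.
- Latest visit: 28 + 7 = day 35. Difference: 35 − 30 = 5 days longer.

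The range applies if the cut-off is read as the actual visit. The 2-day figure applies if it is read as the nominal week.

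**4. How long each mismatch operates**

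- Cut-off: Section 10.3.2 states that all participants had at least 41 weeks of post-treatment follow-up by 18 October 2019. 41 × 7 = 287 days, well past day 35, so only past data can be affected.
- Hepatic category: as planned, from Week 4 to Week 108, 108 − 4 = 104 weeks. After early termination it runs from Week 4 to the EOS visit, whose date is not given. By 18 October 2019 the Synopsis design note (41 to 53 weeks post-treatment) gives 41 − 4 = 37 to 53 − 4 = 49 weeks. The Synopsis schematic note (43 to 51 weeks) gives 39 to 47.

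**The case against.** The strongest reply is that a careful site would report the event anyway. Section 9.2.1 is the full text and is mandatory in tone, Appendix 3 is broader still, and the Table 2-3 note is a table remark in a schedule that Section 9 calls a summary. Two of the three places lead to reporting. This stands in part. A reader might infer that sites would omit required SAEs, but the documents support only that they could, and nothing in them shows that an SAE was missed. The reply does not remove the conflict, because Section 9 also makes adherence to the schedule essential.

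A second reply is that the liver outcomes are captured regardless. This also stands: the hepatic row and its CRF cover every post-treatment visit, so it would be wrong to infer that long-term follow-up fails to detect them. Only the SAE report is exposed.

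A third reply concerns the cut-off. Quoting 9 lost days alone would mislead, because the nominal gap is 2 days and a late visit reverses its direction.

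A reader might also infer that the SAP's SAE tables draw solely on the AE/SAE CRF. SAP Section 6.6.1 names that form only as a source for deaths, and Section 6.6 refers to CRFs in general, so the point does not rest on that inference.

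Finally, the practical reach is very small: 5 participants, required to be non-cirrhotic at entry, with no virologic failure reported by 18 October 2019, and no statistical analyses planned. This is accepted and sets the severity.

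**Conclusion.** The inconsistency is real and lies in current protocol text. After Post-Treatment Week 4 the Table 2-3 note excludes one class of SAE that Section 9.2.1 requires, and no rule of precedence settles it. The class is hepatic-progression SAEs not attributed to drug or procedure, and the exposure lasts until the EOS visit. What could be lost is the 24-hour SAE report and the event's place in the follow-up SAE count; the diagnosis would still be recorded.

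The cut-off mismatch is secondary: nominally 2 days, ranging from 9 days shorter to 5 days longer, and already past for all 5 participants.

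The conclusion assumes that a site might read the note literally. It does not assume that any event occurred or was missed. Severity: minor.

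**What to change.** Reconcile the Table 2-3 note, Section 9.2.1 and Appendix 3 in one statement of which SAEs are reportable and until when, and use the same wording or a cross-reference in all three places. State the end of the all-cause period in one way only, either as a number of days or as a visit.

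At the EOS visit, where SAE and hepatic-progression assessments are already scheduled, have sites confirm that no SAE required by Section 9.2.1 was left unreported. Any diagnosis on the hepatic form should be checked against the SAE reports as part of this.

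The cost is a small wording change and one confirmation per participant, 5 in all. If Revised Protocol 01 is already approved, which the documents do not settle, the change may need IRB/IEC review under the Appendix 2 provisions on protocol revisions. The EOS confirmation adds no visit.
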